6.5 Randomization

[figure not shown]
After eligibility for participants has been confirmed, they will be allocated to a study arm (Investigational or control). Participants will then be randomized accordingly to ensure an equal and unbiased distribution of products. The master randomization list will only be accessible to the designated unblinded personnel at the site until the database is locked. Participants will be given an envelope containing a detailed dosing instruction sheet. They will be instructed to take this home and open it, read and understand the procedure, and contact the site if they have any questions. The contact information for the site will be that of the designated unblinded personnel – these individuals will be able to answer any questions the participants may have about their assigned dosing instructions. Participants will be asked to not disclose information about their assigned dosing instructions to any study staff except the unblinded personnel whose contact information is contained in the detailed dosing instruction sheet.

6.6 Blinding and Unblinding

Blinding of study products will be maintained by appropriately delegated study staff. Designated unblinded personnel will randomize the groups using block randomization ensuring an equal distribution in each group. All site staff (excluding designated unblinded personnel) will remain blinded throughout the study until the data-lock and study-closeout stage.

Since both groups will be receiving identical products (with different instructions of use for each group), emergency unblinding will not be applicable to this trial.

7. Study Design (Flow chart)

8. Planned Study Visits

Pre-Screening Telephone Call:

Potential participants who will be contacted to participate in this study will be pre-screened over the phone. They will be asked a series of questions about their health and lifestyle. As part of that telephone pre-screening the following questions will be asked regarding their allergy symptoms:

- 1- How do you score your nasal congestion (0-5, with 5 being the worst)?
- 2- How do you score your Nasal Discharge or sneezing (0-5, with 5 being the worst)?
- 3- How do you score your watery or itchy eyes (0-5, with 5 being the worst)?
- 4- How many times do you brush your teeth a day (0-3, 0,1,2,3 or more)?
- 5- How many times do you use mouthwash a day (0-2, 0,1,2 or more)?
- 6- How many times do you floss your teeth a day (0-2, 0,1,2 or more)?

Scoring Standards: Total score ≥ 7 in question 1-3 and Total score ≤ 4 in question 4-6 will be booked for Screening (V1). Potential participants with a total score of < 7 in question 1-3 and/or total score > 4 in question 4-6 will not pass the telephone pre-screening and will not be booked for Visit 1.

Visit 1 – Screening

Participants will not be required to fast prior to this visit. The delegated study staff will present the ICF, and review its contents with the participant. The study staff will answer any questions the participant may have.

The Informed Consent Form (ICF) will be provided to the participant. After a sufficient period of reflection, the written and informed consent of the participant will be sought. Each page of the ICF will be initialed and the last page will be signed by the participant. Once signed and attested to by the PI or delegate, a copy of the signed original ICF will be provided to the participant.

After informed consent has been obtained, the PI and/or delegated research site staff will collect demographic information, complete a thorough medical history which will include the review of existing medical records to confirm inclusion/exclusion criteria. Biometric measurements (body temperature, SSH blood pressure, heart rate), anthropometric measurements (height, weight, calculated BMI) will be taken and a short questionnaire to assess allergy symptoms will be conducted. If none of the collected information excludes participation, screening clinical chemistry assessments will be conducted.

The screening information will be reviewed by the PI and/or delegate to determine if the participant is to be scheduled for a physical examination* and a final eligibility assessment.

*Physical exam will be done before dosing. This may be scheduled on another day.

Participants that have met all of the inclusion criteria and none of the exclusion criteria will proceed to the next scheduled visit, and TNSS questionnaire will be administered.

For females of childbearing potential, a urine sample will be collected for a urine pregnancy test.

Blood samples to be collected will be analyzed for the following:

- CBC [Includes: White Blood Cell Count (WBC), Red Blood Cell Count (RBC), Hemoglobin (HB), Hematocrit (HCT), MCV, MCH, MCHC, Platelet Count]
- Aspartate aminotransferase (AST)
- Sodium
- Potassium
- Chloride
- Serum creatinine
- Alanine Amino Transferase (ALT)
- Alkaline Phosphatase (ALP)
- Bilirubin Total
- Gamma Glutamyl Transpeptidase (GGT)

Visit 2 – Baseline – Day 1

These assessments may not be completed in the order shown below.

Participants:

1. Must be at least 8 hours fasting (no food, only water) prior to visit.
2. Will have any changes to health reviewed by delegated study staff.
3. For females of childbearing potential, a urine sample will be collected for a urine pregnancy test.
4. Will have the following measurements taken: temperature, blood pressure, heart rate.

5. Will have the following saliva test:
 - Amplicon Metagenomics Sequencing
6. Will complete the following assessments:
 - Total nasal symptoms score (TNSS) questionnaire (appendix 2).
 - Peak nasal inspiratory flow (PNIF) measurement.
7. Will have the following blood tests:
 - CBC (WBC, RBC, Hb, HCT, MCV, MCH, MCHC, Platelet Count)
 - Aspartate aminotransferase (AST)
 - Alanine aminotransferase (ALT)
 - Bilirubin
 - Gamma-glutamyl transferase (GGT)
 - Alkaline phosphatase (ALP)
 - Serum creatinine
 - Potassium
 - Chloride
 - Sodium
 - IgE (total)
8. Be provided with a paper/electronic diary – IP dosing, adverse events, concomitant medication.
9. Be provided with the IP (and oral hygiene kit if applicable) and instructions on dosing.
10. Be provided with dates/times of subsequent visit(s).
11. Review of all information for the visit by the PI and/or delegate prior to the next study visit to determine continued safe participation.

The participant will be given a paper/electronic daily diary in order to record the use of concomitant medications, IP dosing, symptoms, and any adverse events (such as fatigue, fever or headache) that may have occurred. The diary will be collected and/or reviewed at the research site at each visit as indicated on the Schedule of Assessments.

The participant should take the IP after this visit at home. The participant should take AllerPops at a maximum frequency of once every other day until the next study visit (Day 7). The participant should not take the product the morning of the next visit. The designated maximum dose until the next visit on day 7, is 3 doses.

Visit 3 – Follow-Up – Day 7 ± 1

These assessments may not be completed in the order shown below.

Participants:

1. Must be at least 8 hours fasting (no food, only water) prior to visit.
2. Will have any changes to health reviewed by delegated study staff.
3. Study diary will be collected and/or reviewed by delegated study staff for completion, and any AEs and/or concomitant medications.
4. For females of childbearing potential, a urine sample will be collected for a urine pregnancy test.

5. Will have the following measurements taken: temperature, blood pressure, heart rate.
6. Will have the following saliva test:
 - Amplicon Metagenomics Sequencing
7. Will complete the following assessments:
 - Total nasal symptoms score (TNSS) questionnaire
 - Peak nasal inspiratory flow (PNIF) measurement
8. Will have the following blood tests:
 - CBC (WBC, RBC, Hb, HCT, MCV, MCH, MCHC, Platelet Count)
 - Aspartate aminotransferase (AST)
 - Alanine aminotransferase (ALT)
 - Bilirubin
 - Gamma-glutamyl transferase (GGT)
 - Alkaline phosphatase (ALP)
 - Serum creatinine
 - Potassium
 - Chloride
 - Sodium
 - IgE (total)
9. Be reminded to complete daily diary.
10. Review of all information for the visit by the PI and/or delegate prior to the next study visit to determine continued safe participation.

After completion of treatment dose, the participants are allowed for extra 4 maintenance doses, at a maximum frequency of once every other day (on day 7, 9, 11, and 13). Participant will not take the product on day 14 and onwards, and must return all remaining product at visit 4. Between day 7 and day 13, the participants may take AllerPops with any recurrence of nasal allergy symptoms or until the participant is satisfied with the relief of the nasal allergy symptoms, as long as the minimal interval of alternate day dosing is not violated. The participant will continue to fill out a daily diary to indicate the time of dosing, symptoms, AEs (such as fatigue, fever or headache), and concomitant medications, if applicable.

Visit 4 – Follow-Up – Day 14 ± 2

These assessments may not be completed in the order shown below.

Participants:

1. Do not need to fast prior to this visit.
2. Will have any changes to health reviewed by delegated study staff.
3. Study diary will be collected and/or reviewed by delegated study staff for completion, and any AEs and/or concomitant medications.
4. Will have the following measurements taken: temperature, blood pressure, heart rate.
5. Will complete the following assessments:
 - Total nasal symptoms score (TNSS) questionnaire
 - Peak nasal inspiratory flow (PNIF) measurement
6. Be reminded to complete daily diary.

The participant will continue to fill out a daily diary to indicate symptoms, AEs (such as fatigue, fever or headache), and concomitant medications, if applicable.

After this visit, the participant will not continue taking the IP. Any remaining IP will be collected from the participant at this visit.

Visit 5 – End of Study – Day 21 ± 2

These assessments may not be completed in the order shown below.

Participants:

1. Must be at least 8 hours fasting (no food, only water) prior to visit.
2. Will have any changes to health reviewed by delegated study staff.
3. Study diary will be collected and reviewed by delegated study staff for completion, and any AEs and/or concomitant medications.
4. For females of childbearing potential, a urine sample will be collected for a urine pregnancy test.
5. Will have the following measurements taken: temperature, blood pressure, heart rate.
6. Will have the following saliva test:
 - Amplicon Metagenomics Sequencing
7. Will complete the following assessments:
 - Total nasal symptoms score (TNSS) questionnaire
 - Peak nasal inspiratory flow (PNIF) measurement
8. Will have the following blood tests:
 - CBC (WBC, RBC, Hb, HCT, MCV, MCH, MCHC, Platelet Count)
 - Aspartate aminotransferase (AST)
 - Alanine aminotransferase (ALT)
 - Bilirubin
 - Gamma-glutamyl transferase (GGT)
 - Alkaline phosphatase (ALP)
 - Serum creatinine
 - Potassium
 - Chloride
 - Sodium
 - IgE (total)
9. Review of all information for the visit by the PI and/or delegate to determine further action, if necessary.

The results of the clinical chemistry will be assessed by the PI. The clinical chemistry parameters must be within the reference value ranges and/or deemed by the PI as not clinically significant. Otherwise, the participant will be contacted by the PI or delegated site staff to further assess and determine an appropriate course of action.

9. Clinical Assessments and Procedures

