15.2.	Informed Consent Form.....	343
15.3.	Risks and Procedures to Minimize Risk.....	343
16.	Quality Assurance and Quality Control	35
16.1.	Auditing.....	354
16.2.	Monitoring.....	34
16.3.	Data Management.....	354
17.	References.....	37
18.	Appendix 1: Questionnaires.....	40

1. List of Abbreviations

ADA	Anti-Drug Antibodies
ADR	Adverse Drug Reaction
AE	Adverse Event
ALT	Alanine aminotransferase
ANOVA	Analysis of Variance
AST	Aspartate aminotransferase
BMI	Body Mass Index
BPM	Beats per minute
BUN	Blood urea nitrogen
CBC	Complete Blood Count
CRF	Case Report Form
CTMS	Clinical Trial Management Software
Cl	Chloride
Cr	Creatinine
eCRF	Electronic Case Report Form
EDTA	Ethylenediaminetetraacetic acid
ET	Early Termination
GCP	Good Clinical Practices
GLP	Good Laboratory Practices
GMP	Good Manufacturing Practices
GGT	Gamma glutamyl transpeptidase/transferase
h or hr	Hour
HCT	Hematocrit
Hb	Hemoglobin
HIV	Human Immunodeficiency Virus
ICF	Informed Consent Form
ICH	International Council for Harmonisation
ID	Identification
IP	Investigational Product
IRB	Institutional Review Board
IUD	Intrauterine Device
K	Potassium
Kg	kilogram
m	Meter
MCH	Mean corpuscular hemoglobin
MCHC	Mean corpuscular hemoglobin concentration
MCV	Mean corpuscular volume
Na	Sodium
NCS	Not clinically significant
OTC	Over the counter
PD	Protocol Deviation
PI	Principal Investigator
PV	Protocol Violation
RBC	Red Blood Cell
SAE	Serious Adverse Event

SAP	Statistical Analysis Plan
SOP	Standard Operating Procedure
WBC	White Blood Cell
EDA	Exploratory Data Analysis

2. Protocol Synopsis

Title: A randomized, double-blind, controlled, single-centre, 21-day study to investigate the efficacy of AllerPops to reduce nasal symptoms in adult volunteers with seasonal/year-long nasal allergies.

Phase: Phase II

Duration: Up to 30 days between Screening (V1) and Baseline (V2), and a 21-day intervention period, with dosing occurring every other day for a minimum of 3 doses, and thereafter until the participant is satisfied with the relief of the nasal allergy symptoms. The suitable season for the trial will be determined based on the seasonal variation measures.

Primary Objectives: To assess the effectiveness of AllerPops on relieving nasal symptoms compared to the control group in volunteers with seasonal/year-long allergies during the first 7 days of the 21-day intervention period.

Secondary Objective:

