2.1. Inclusion Criteria

Participants must meet all of the following criteria to be considered eligible for admission to the study.

1. Participants will be clinically diagnosed with persistent or intermittent allergic rhinitis, according to the Allergic Rhinitis and Its Impact on Asthma (ARIA) classification. (The guidelines of Allergic Rhinitis and its Impact on Asthma (ARIA) group, classified it to intermittent (less than 4 days per week and for less than 4 weeks) and persistent (more than 4 days per week or lasting more than 4 weeks regardless of the number of days per week).
2. Male or female seasonal/year-long nasal allergy sufferers (as assessed by a questionnaire at screening) between the ages of 18 and 70.

3. Females who are not of childbearing potential (post-menopausal defined as those with amenorrhea for at least 2 years). Females of childbearing potential should be either sexually inactive (abstinent) for 60 days prior to the first dose of the study, throughout the study and for 30 days after completion of the study, or be using one of the following acceptable methods of birth control:
 - i. Surgically sterile (bilateral tubal-ligation, hysterectomy, bilateral oophorectomy) for at least 90 days prior to the first dose of the study.
 - ii. IUD in place for at least 60 days prior to the first dose of the study, throughout the study and for 30 days after completion of the study.
 - iii. Barrier methods (condom, diaphragm) with spermicide for at least 60 days prior to the first dose of the study, throughout the study and for 30 days after study completion.
 - iv. Hormonal contraceptives for at least 90 days prior to the first dose of the study, throughout the study, and for 30 days after study completion.

*Changes to the method of birth control while participating in the study will be judged by the PI for acceptability.

4. Written informed consent obtained and signed by participant.
5. BMI between 18.5 and 29.9 kg/m², with a stable weight over the last 3 months. (A stable weight is defined as <5% of total body weight change in the last 3 months).
6. Agrees not to use any over the counter, prescription, health supplement or dietary supplement from at least 14 days prior to screening until the end of the study.
7. Agrees to maintain current dietary habits, level of physical activity, occupational and living environment for the trial duration.

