For the control group, the same investigational product will be administered, however the procedure for use will be modified as follows: There will be no mouth cleaning before the product consumption (No step 1 as mentioned above). The product will be swallowed instead of dissolved in the mouth, in order to reduce its presence in the mouth as much as possible. The purpose of this control group is to support the effect of use of the entire two-step method as compared to the investigational group.

The active ingredient, L-Arginine is known to Health Canada. L-Arginine is listed in the NHPID, and allowed for use in NHPs under proposed here conditions of use. Safety of the of current ingredient combination, while allowed for use separately, will also be tested under proposed conditions of use.

The Rationale for Performing Research:

Increase in immune-mediated conditions [30]–[32](Allergic rhinitis is one of them) and the few medical solutions available (each of which is associated with side effects) prompted this research and clinical study. The medicinal ingredient, L-Arginine, in the formulation of AllerPops is a well-known Natural Health Product Ingredient with history of human use.

4. Study Objectives

Objectives:

Primary Objective: To assess the effectiveness of AllerPops on relieving nasal symptoms compared to the control group in volunteers with seasonal and perennial (or intermittent and persistent) allergic rhinitis during the first 7 days of the 21-day intervention period.

Secondary Objectives:

1. To evaluate the safety of AllerPops administration in volunteers with seasonal/year-long allergies during a 21-day intervention period.
2. To assess the duration of effectiveness of AllerPops in relieving nasal symptoms compared to the control group in volunteers with seasonal/year-long allergies during a 21-day intervention period (exploratory).

3. To evaluate the effect of the AllerPops administration on the oral microbial presentation/microbiota using Amplicon Metagenomics Sequencing test through saliva samples during a 21-day intervention period (exploratory).
4. To evaluate the effect of the AllerPops administration on the IgE (total) blood level during a 21-day intervention period (exploratory).

Endpoints:

Primary Endpoint: The reduction of nasal allergic symptoms during the first 7 days of the 21-day intervention period (once every other day – D1, D3, D5). The reduction of symptoms will be measured using the following assessments.

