11.1. Determination of Sample Size

Seventy-two participants will be participating in the study. The sample size was chosen based on the G*Power calculator in order to detect an effect of 0.6 (Medium effect size) considering 80% power in t tests. Parametric statistical techniques including, but not limited to t tests -

Means: Difference between two independent means (two groups) will be performed on data sets which meet all requirements for normality and variance. The application of non-parametric techniques might be used for relevant data sets. Should any of the statistical methods proposed prove unsuitable during the final analysis, more appropriate methods will be used, and any changes will be documented in the clinical study report, including the rationale for use. These include the transformation of the data (for example to a logarithmic scale) in order to satisfy model assumptions, if applicable. A p-value of < 0.05 will indicate statistical significance for all tests. An exploratory data analysis (EDA) will be performed for the exploratory study part to analyze and investigate data sets and summarize the main characteristics, employing data visualization methods.

[figure not shown]

Figure 1: Analysis: A priori: Compute required sample size.

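### The primary Day 7 comparison ignores rhinitis class (intermittent or persistent), although inclusion 1 enrols both; adjusting for class protects power at almost no cost

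*Combined protocol and SAP*

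**What the plan says.** **Population.** Inclusion 1 (Sections 2.1 and 5.1) requires a diagnosis of persistent or intermittent allergic rhinitis. The ARIA scheme, as the synopsis words it, "classified it to intermittent (less than 4 days per week and for less than 4 weeks". Persistent means more than 4 days per week or more than 4 weeks. The primary objective in Section 4 names the mixture: "seasonal and perennial (or intermittent and persistent) allergic rhinitis".

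**Allocation.** Section 6.6: "Designated unblinded personnel will randomize the groups using block randomization ensuring an equal distribution in each group". The text of 6.5 and 6.6 gives no stratification factor and no block size. The figure in 6.5 is not shown.

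**Analysis.** Section 11.3.1 compares the Day 1 to Day 7 change in TNSS and PNIF within and between groups. Section 11.3.3 assigns parametric or non-parametric tests for independent or related samples. No covariate or stratified analysis is mentioned, and no summary by rhinitis class.

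**Size.** Section 11.1: "Seventy-two participants will be participating in the study", chosen "in order to detect an effect of 0.6 (Medium effect size) considering 80% power in t tests". The significance rule is "A p-value of < 0.05 will indicate statistical significance for all tests".

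**Timing.** The synopsis allows "Up to 30 days between Screening (V1) and Baseline (V2").

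**The concern.** Blocking equalises the arm totals, not the make-up of the arms. Class is one baseline characteristic that the protocol itself singles out, and it is defined by how often and for how long symptoms occur. It could plausibly predict the change in symptoms over a week.

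If it does, two things follow from leaving it out of the analysis. The between-class variation stays in the error term, so the test is less powerful than it could be with the same 72 people. And if the arms happen to differ in class mix, the estimate carries that difference with nothing in the plan to correct it.

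A second problem needs no assumption. As written, the two definitions do not cover everyone. Symptoms on exactly 4 days a week for less than 4 weeks fit neither class, and neither do symptoms on up to 4 days a week for exactly 4 weeks. Since inclusion 1 requires one class or the other, eligibility is also unclear for these people.

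**Working it through.** **Inputs from the documents:** N = 72, taken as 36 per arm (11.1, with equal groups from 6.6); standardised effect 0.6; power 80%; t test of two independent means; significance level 0.05 (11.1).

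**Assumptions, because the documents are silent:** share intermittent p = 20-50%; difference between classes in mean Day 7 change g = 0.5, 1.0 or 1.5 within-class SD; true effect 0.6 within-class SD; blocks of 4; two-sided testing.

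**1. The plan's own figure.** Noncentral-t power for d = 0.6 and level 0.05 gives 36 per arm, total 72, for a one-sided test (power 80.9%). A two-sided test needs 45 per arm, total 90, and has 70.9% power at 72. Sidedness is not stated in the text and the sample-size figure is not shown, so that is a separate matter. The figures below start from the two-sided 70.9%.

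**2. What ignoring class does to power.** The unadjusted SD is √(1 + p(1−p)g²), so the effective effect is 0.6/√(1 + p(1−p)g²). At p = 0.5:
- g = 0.5: 0.6/√1.0625 = 0.582
- g = 1.0: 0.6/√1.25 = 0.537
- g = 1.5: 0.6/√1.5625 = 0.480

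Simulation of the t test against a linear model with arm and class, 15,000 trials per scenario:

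| p | g | Unadjusted power | Adjusted power |
|---|---|---|---|
| 0.5 | 0.5 | 68.0% | 70.2% |
| 0.5 | 1.0 | 61.4% | 70.7% |
| 0.5 | 1.5 | 50.6% | 70.3% |
| 0.3 | 1.0 | 62.6% | 70.7% |

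Over 40-50% intermittent, the ranges are about 68% to 69-70% for g = 0.5 and about 60-61% to 69-71% for g = 1.0. With g = 0, adjustment costs under 1 point. None of this counts any gain from the Day 1 value.

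**3. Type I error.** Averaged over randomisations, the unadjusted test rejects a true null in 4.6-5.2% of trials. There is no inflation.

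**4. Imbalance in a single trial.** With K intermittent among 72, the number allocated to one arm of 36 is hypergeometric. The SD of the between-arm difference in share intermittent is 9.4, 10.9 and 11.9 percentage points for p of about 20%, 30% and 50%. A gap of 20 points or more has probability 3.5%, 7.2% and 9.8%. A 20-point gap moves the arm difference by 0.20 × g, that is 0.10, 0.20 or 0.30 SD for the three values of g. The standard error of the arm difference is √(2/36) = 0.236 SD.

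Conditional on a gap of at least 20 points at p = 0.5, unadjusted false positives are 7%, 15% and 20% for g = 0.5, 1.0 and 1.5. If a gap of that size goes against the investigational arm, unadjusted power is 53%, 22% and 8%, against about 67-74% adjusted.

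**5. Stratified blocks or adjustment?** At p = 0.5, g = 1.0:

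| Design and analysis | Type I error | Power |
|---|---|---|
| Unstratified, unadjusted (plan) | 5.1% | 61% |
| Stratified, unadjusted | 2.8% | 62% |
| Unstratified, adjusted | 5.0% | 71% |
| Stratified, adjusted | 5.0% | 71% |

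Nearly all the gain comes from the analysis. Stratifying without adjusting adds about 1 point and makes the test conservative.

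**The case against.** A reader might infer that intermittent disease resolves by itself, so that an unstratified allocation can manufacture or conceal the Day 7 result. The documents do not support that reading.

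- Nothing in them calls intermittent disease self-resolving. The definition has two limbs, days per week and weeks, and is a classification, not a prognosis. That an episode of under 4 weeks could end within a screening gap of up to 30 days, or during follow-up, is an inference.
- The direction is open. The TNSS form in Appendix 1 asks about the last week. An episode over well before Day 1 would give a low Day 1 score with little room to improve, so such participants might improve less, and the Day 1 score would carry part of the difference.
- Chance imbalance is random error, which the unadjusted test already counts on average. The conditional error rates above apply only after an unlucky draw.
- The size rests on two unknowns. With 20% intermittent and a 0.5 SD gap, even a 1.96-SD imbalance moves the result by only 0.09 SD.
- Choosing the season from seasonal variation measures (synopsis), and requiring a telephone pre-screening total of at least 7 on the three symptom questions (Section 8), both limit entry of people with few current symptoms.
- Unstratified blocks are a legitimate choice in a single-centre trial of 72.

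All of this stands, and it removes any claim of bias and any need to insist on stratification. It does not defend leaving class out of the analysis. A further objection is that class at Visit 1 may be out of date by Visit 2. That weakens its predictive value, but it is still a pre-randomisation covariate and adjusting for it is valid.

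**Conclusion.** The concern holds as one about efficiency and about robustness in the single trial, not about validity. The plan enrols two classes, states no stratification by them, and compares arms without using them. Under the assumptions above, adjustment is worth roughly 1 to 2 points of power at a 0.5 SD class gap and about 9 at 1.0 SD, and it guards against a draw of 20 points or more that has about a 3-10% chance. If class predicts nothing, the loss is under 1 point. Since the mix and the gap are not in the documents, the benefit may turn out small, but the exchange favours adjustment. The gaps in the class definitions are a plain defect, independent of any assumption.

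**What to change.** - **Section 11.3:** make the primary between-arm comparison of TNSS and PNIF at Day 7 a linear model (ANCOVA) with arm, the Day 1 value and ARIA class at screening as terms. Report the arm-by-class counts.
- **Visit 1 and CRF:** record the class for each participant. The Visit 1 procedures list medical history and a short allergy questionnaire, but do not explicitly call for the class to be recorded.
- **Inclusion 1 (2.1 and 5.1):** reconcile the two definitions so that every participant falls in exactly one class. Where the boundary cases belong is for the clinical team to decide.
- **Sections 6.5 and 6.6 (optional):** permuted blocks within class, only if paired with the adjusted analysis.

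Cost: one model term, one degree of freedom and one CRF field. Optional stratification adds a second randomisation list and possibly an incomplete block in each stratum.
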